4.0 Treatment Plan

Patients will be treated in cycles of 28 days (±3 days). Patients will receive romidepsin (at a dose of either 10 or 14 mg/m² – see 4.1.1 for details) IV on days 1, 8, and 15 as well as lenalidomide 25 mg PO daily on days 1- 21 of each cycle. Treatment may continue for one year or until disease progression or unacceptable toxicity. Patients who do not achieve a response of PR or better should continue to be treated only if they have SD (i.e., not PD), and if they do not have other options available that would present a more favorable risk/benefit ratio. Clinical suspicion of progressive disease (PD) or loss of response should be investigated radiographically (or by repeat bone marrow biopsy for marrow-only disease), and if confirmed, will result in removal from active therapy; such patients will remain in study follow up. In this case, it is strongly recommended that investigators consider early initiation CHOP or similar chemoimmunotherapy (off trial).

Treatment will be based on weight at baseline. Dosing should only be modified if the patient's weight has changed by more than 10% from baseline or the BSA has changed more than 5%.

It is intended that all treatments will be administered on an outpatient basis. However, treatment can be initiated during hospitalization (i.e., for newly-diagnosed patients), and can continue during unforeseen hospitalizations, but only at the discretion of the local primary investigator (PI).

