4.3 Concomitant Medications/Treatments

be in the best interest of the patient.

NOTE: No other treatment modalities or procedures are required as part of the study treatment. Any patient receiving radiation therapy and/or surgery related to progression of malignancy will be removed from protocol therapy. In addition, any patient that subsequently undergoes stem cell transplant will be removed from protocol therapy.

4.3.1 Recommended concomitant medications include:

- 5-HT3 receptor antagonist (such as Zofran 16 mg IVPB or equivalent dose) prior to romidepsin infusions
- Dexamethasone 10 mg IVPB (or similar) prior to romidepsin infusions

4.3.2 Permitted concomitant medications:

- Symptomatic treatment as needed for nausea, vomiting, and/or diarrhea, including 5-HT3 antagonists, corticosteroids, benzodiazepines, and antimotility agents
- Topical and systemic treatment for rash, including corticosteroids.
- Hormonal birth control medications.
- Concurrent antiviral therapy for HBV surface antigen positivity.
- Corticosteroids are permitted for any indication other than to treat lymphoma
- Transfusions and growth factor are permitted at physician discretion and per institutional guidelines.

4.3.3 Prohibited concomitant medications and treatments:

• Concurrent chemotherapy, radiotherapy, or other investigational agents.

NOTE: Radiotherapy is permitted to treat a single non-target lesion for symptom control.

- Corticosteroids intended to treat lymphoma (NOTE: There is no washout for prior corticosteroid treatment of lymphoma, however patients may not have received such corticosteroids for >10 days)
- CYP3A4 inducers (see appendix C) Note: As this list is constantly evolving, if a medication is incorrectly documented as prohibited in this protocol, documentation from the site pharmacist to the contrary will be acceptable for the purposes of registration.
- High risk QTc prolonging agents in the case of patients who have developed QTc prolongation on study (see appendix C)

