6.2.1 Complete Remission (CR)

CR requires the following:

Complete disappearance of all detectable clinical evidence of disease and disease-related symptoms if present before therapy.

1. Typically FDG-avid lymphoma: in patients with no pretreatment PET scan or when the PET scan was positive before therapy, a post-treatment residual mass of any size is permitted as long as it is PET negative.

Variably FDG-avid lymphomas/FDG avidity unknown: in patients without a pretreatment PET scan, or if a pretreatment PET scan was negative, all lymph nodes and nodal masses must have regressed on CT to normal size (\leq 1.5 cm in their greatest transverse diameter for nodes > 1.5 cm before therapy). Previously involved nodes that were 1.1 to 1.5 cm in their long axis and more than 1.0 cm in their short axis before treatment must have decreased to \leq 1.0cm in their short axis after treatment.

- 2. The spleen and/or liver, if considered enlarged before therapy on the basis of a physical examination or CT scan, should not be palpable on physical examination and should be considered normal size by imaging studies, and nodules related to lymphoma should disappear. However, determination of splenic involvement is not always reliable because a spleen considered normal in size may still contain lymphoma, whereas an enlarged spleen may reflect variations in anatomy, blood volume, the use of hematopoietic growth factors, or causes other than lymphoma.
- 3. If the bone marrow was involved by lymphoma before treatment, the infiltrate must have cleared on repeat bone marrow biopsy. The biopsy sample on which this determination is made must be adequate (with a goal of > 20 mm unilateral core). If the sample is indeterminate by morphology, it should be negative by immunohistochemistry. A sample that is negative by immunohistochemistry but that demonstrates a small population of clonal lymphocytes by flow cytometry will be considered a CR until data become available demonstrating a clear difference in patient outcome.

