6.2.2 Partial Response (PR)

PR requires the following:

- At least a 50% decrease in sum of the product of the diameters (SPD) of up to six of the largest dominant nodes or nodal masses. These nodes or masses should be selected according to all of the following: they should be clearly measurable in at least 2 perpendicular dimensions; if possible they should be from disparate regions of the body; and they should include mediastinal and retroperitoneal areas of disease whenever these sites are involved.
- 2. No increase should be observed in the size of other nodes, liver, or spleen.

- 3. Splenic and hepatic nodules must regress by ≥ 50% in their SPD or, for single nodules, in the greatest transverse diameter.
- 4. With the exception of splenic and hepatic nodules, involvement of other organs is usually assessable and no measurable disease should be present.
- 5. Bone marrow assessment is irrelevant for determination of a PR if the sample was positive before treatment. However, if positive, the cell type should be specified (e.g., large-cell lymphoma or small neoplastic B-cells). Patients who achieve a CR by the above criteria, but who have persistent morphologic bone marrow involvement will be considered partial responders. When the bone marrow was involved before therapy and a clinical CR was achieved, but with no bone marrow assessment after treatment, patients should be considered partial responders.
- 6. No new sites of disease should be observed.
- 7. Typically FDG-avid lymphoma: for patients with no pretreatment PET scan or if the PET scan was positive before therapy, the post-treatment PET should be positive in at least one previously involved site.

Variably FDG-avid lymphomas/FDG-avidity unknown: for patients without a pretreatment PET scan, or if a pretreatment PET scan was negative, CT criteria should be used.

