6.2.4 Relapsed Disease (after CR) or Progressive Disease (after PR or SD)

- Lymph nodes should be considered abnormal if the long axis is more than 1.5 cm regardless of the short axis. If a lymph node has a long axis of 1.1 to 1.5 cm, it should only be considered abnormal if its short axis is more than 1.0. Lymph nodes ≤ 1.0 x ≤ 1.0 cm will not be considered as abnormal for relapse or progressive disease.
- 2. Appearance of any new lesion more than 1.5 cm in any axis during or at the end of therapy, even if other lesions are decreasing in size. Increased FDG uptake in a previously unaffected site should only be considered relapsed or progressive disease after confirmation with other modalities. In patients with no prior history of pulmonary lymphoma, new lung nodules identified by CT are mostly benign. Thus, a therapeutic decision should not be made solely on the basis of the PET without histologic confirmation.
- 3. At least a 50% increase from nadir in the SPD of any previously involved nodes, or in a single involved node, or the size of other lesions (e.g., splenic

or hepatic nodules). To be considered progressive disease, a lymph node with a diameter of the short axis of less than 1.0 cm must increase by \geq 50% and to a size of 1.5 x 1.5 cm or more than 1.5 cm in the long axis.

- 4. At least a 50% increase in the longest diameter of any single previously identified node more than 1 cm in its short axis.
- 5. Lesions should be PET positive if observed in a typical FDG avid lymphoma or the lesion was PET positive before therapy unless the lesion is too small to be.

Response	Definition	Nodal Masses	Spleen, Liver	Bone Marrow
CR	Disappearance of all evidence of disease	 (a) FDG-avid or PET positive prior to therapy; mass of any size permitted if PET negative (b) Variably FDG-avid or PET negative; regression to normal size on CT 	Not palpable, nodules disappeared	Infiltrate cleared on repeat biopsy; if indeterminate by morphology, immunohistochemistry should be negative

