		calculating Creatinine	
		Clearance	
	Patients must be free of	Adds that "free of prior	To clarify prior confusion as
3.1.8 (Inclusion Criteria)	any prior malignancies for	malignancies" is at the	to the definition of
	≥1 year	investigator's discretion.	malignancy free
	n/a	Excludes patients who are	To address clarification
		receiving concurrent	brought up by an affiliate
226 (Evolution Critoria)		minunosuppressive	sile. It is not clinically
3.2.0 (Exclusion Chiena)			
			medications with the study
			treatment.
4.2 (Toxicities, Dosing	n/a	Adds: "If study drug is	Clarification; there was
Delays, and Dose		delayed more than 21 days	previously no language
Madifications)		(1 treatment cycle)	about maximum length of

		treatment may be discontinued after discussion with the PL"	holding patients for toxicity.		
4.3.2 (Permitted Concomitant Medications)	n/a	Transfusions and growth factor are clarified to be permitted at physician discretion and per institutional guidelines	Clarification requested by affiliate site; transfusion and growth factor were not previously mentioned		
4.3.3 (Prohibited Concomitant Medications & Treatments)	Concurrent radiotherapy was generally prohibited	Adds a stipulation that radiotherapy is permitted to treat a single non-target lesion for symptom control	Clarification resulting from a clinical situation. Patients should be permitted to receive radiotherapy separate from the disease target lesions as it does not affect disease assessments or study endpoints		
4.6 (Patient Replacement); 4.7 (Suspension of Accrual); 7.3 (Expedited Reporting of SAEs) 11.10 (Publication Policy); 11.11 (Criteria for Suspension in Accrual)	Referenced Data Monitoring Committee (DMC)	Updates to reference Data and Safety Monitoring Committee (DSMC)	Administrative update to align with internal policies		
5.0 (Study Procedures, #8)	n/a	SAE's are to be collected from the time of consent until 30 days after treatment	Clarification for easier referencing to align with SAE timelines within the protocol		
7.2.3 (Serious Adverse Events)	SAE's were to be collected during the study and for 30 days after treatment	Adds that SAE's will be collected from the time of consent until 30 days after treatment	Clarification requested by affiliate site		
	Amendment SRC-approved of	t 8 – July 5, 2019 on December 6, 2019			
Section(s) Affected	Prior Version	Amendment 8 Changes	Rationale		

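### On-study radiotherapy is allowed to one undefined non-target lesion, yet such a lesion can decide CR, block PR or trigger PD, and no rule says how to score it

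*Combined protocol and SAP*

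**What the plan says.** Section 4.3.3 lists concurrent radiotherapy as prohibited, then makes an exception: "Radiotherapy is permitted to treat a single non-target lesion for symptom control". It sets no time limit, requires no scan beforehand and gives no scoring rule. The Amendment 7 entry in Appendix E records the premise, namely that patients should be able to receive "radiotherapy separate from the disease target lesions as it does not affect disease assessments or study endpoints".

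The response rules in Section 6.2 never use the term target lesion. The nearest concept is in the PR rule (6.2.2), which asks for a fall of at least half in the SPD "of up to six of the largest dominant nodes or nodal masses". Other lesions also count:

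- CR (6.2.1): "Complete disappearance of all detectable clinical evidence of disease and disease-related symptoms if present before therapy".
- PR (6.2.2): "No increase should be observed in the size of other nodes, liver, or spleen". Measurable disease in other organs also rules out PR.
- PD (6.2.4): "At least a 50% increase from nadir in the SPD of any previously involved nodes, or in a single involved node".

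Two provisions bear on the gap. Section 4.3 says: "Any patient receiving radiation therapy and/or surgery related to progression of malignancy will be removed from protocol therapy". Section 4.0 says: "Clinical suspicion of progressive disease (PD) or loss of response should be investigated radiographically". Neither says how response, PFS or duration of response is then scored, and Section 10 is silent on radiotherapy.

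**The concern.** The exception rests on the idea that a lesion outside the target set does not matter for the endpoints. Under Section 6.2 it does. A symptomatic lesion is the kind most likely to be irradiated, and it may also be the one that stands between the patient and a CR or PR, or the one about to meet PD. If local treatment removes it, the next assessment credits the result to romidepsin plus lenalidomide.

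The mechanism favours the regimen, and a single-arm trial has no control group to offset it. The ORR, the stopping decision in Section 7.4, the CR rate, PFS and duration of response are exposed, though not equally. Because target is undefined, the text does not clearly exclude even one of the measured masses.

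**Working it through.** **Step 1. The rules applied to cases.** Take a patient whose irradiated lesion lies outside the measured masses.

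| Situation | Without radiotherapy | After radiotherapy | Endpoints that can move |
|---|---|---|---|
| Measured masses not halved | Not PR | Not PR | ORR cannot move |
| Measured masses halved; another node has grown, short of PD | Not PR | PR possible | ORR, interim count |
| Measured masses halved; measurable disease in another organ | Not PR | PR possible | ORR, interim count |
| All else meets CR; one lesion remains | PR | CR possible | CR rate and CR duration only |
| A node is growing towards the PD threshold | PD at a later scan | PD not reached | PFS, duration of response; ORR only if the measured masses have halved |

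Radiotherapy outside the measured set therefore removes a blocker. It does not produce a PR alone.

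**Step 2. Timing.** Section 5.0 (Table 4, note 12) schedules scans after cycles 3 and 6, then every 6 months, with extra scans if clinically indicated. Three cycles are 3 × 28 = 84 days. A lesion irradiated before the cycle 3 scan, with no unscheduled scan, has only its baseline measurement on record, so any growth is never documented.

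**Step 3. The plan's precision figure.** Section 10.1 gives a half-width of 0.22 at n=20. Check: 1.96 × 0.5/√20 = 0.219, which agrees.

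**Step 4. Effect of one reclassified patient.**

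- Final ORR: 1/20 = 5.0 points. For example, 10/20 = 50% (exact 95% CI 27.2 to 72.8%) becomes 11/20 = 55% (31.5 to 76.9%).
- Interim: 1/12 = 8.3 points. Section 7.4 stops at 6 or fewer of 12. At a true ORR of 50% (the rate Section 10.1 cites for the combination in relapsed or refractory disease), P(exactly 6 of 12) = C(12,6) × 0.5^12 = 924/4096 = 22.6%. In those trials a single reclassification turns stop into continue.

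**Step 5. Range under assumptions.** The documents do not give the share q of true non-responders who would be reclassified. Assume 5%, 10% or 20%. Apparent ORR = p + (1 − p)q, and the chance of continuing is P(X ≥ 7) for X binomial with n=12.

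| True ORR p | q = 0 | q = 5% | q = 10% | q = 20% |
|---|---|---|---|---|
| 40%: apparent ORR | 40% | 43% | 46% | 52% |
| 40%: P(continue) | 15.8% | 21.6% | 28.4% | 44.2% |
| 50%: apparent ORR | 50% | 52.5% | 55% | 60% |
| 50%: P(continue) | 38.7% | 45.6% | 52.7% | 66.5% |

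These rows show sensitivity only. They do not estimate how often reclassification would happen.

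**The case against.** The strongest reply is that overt progression is already handled. A painful, growing node gives clinical suspicion of PD, which Section 4.0 says to image, and Section 4.3 takes a patient irradiated for progression off protocol therapy. This stands in part. What remains is a lesion that grows by less than the PD threshold, or that is irradiated for symptoms before anyone images it. Nor are these two provisions analysis rules: leaving therapy does not settle how response or PFS is scored.

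Three stronger readings are tempting, and the documents do not support them.

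- A reader might infer that radiotherapy can manufacture a PR. It cannot if the lesion is outside the measured set, because the SPD of the measured masses must still halve. Moving a patient from PR to CR leaves the ORR and the interim count unchanged, since both count CR or PR.
- A reader might infer that Sections 4.3 and 4.3.3 contradict each other. They name different indications, progression and symptom control. The difficulty is that the boundary is undefined: a symptomatic, enlarging lesion could fit either, and the consequences are opposite.
- A reader might take 5 to 10 points as the expected bias with one or two irradiated patients. An irradiated patient may respond anyway, or may fail the SPD criterion regardless, and neither moves the ORR.

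The Amendment 7 rationale is a log entry and is not counted as a separate error. It matters only because it states the premise behind a note that is still current.

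**Conclusion.** The point holds in limited form. A plan that allows radiotherapy to a lymphoma lesion, leaves target undefined, lets lesions outside the measured masses decide response and progression, and has no scoring rule can credit a local treatment effect to the study drugs.

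The size is known only per patient: 5 points of ORR at n=20 and 8.3 points at the interim for each patient truly reclassified. For one to two irradiated patients, 5 to 10 points is therefore the ceiling on the final ORR. The total bias cannot be derived, because neither the frequency of radiotherapy nor the share reclassified is given. The interim result is the most fragile, because one patient can reverse the decision. No view is taken on whether radiotherapy should be allowed.

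**What to change.** These changes concern definitions, data capture and analysis.

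1. In Section 6.2, define target lesions and require them to be identified at baseline.
2. Record the date, site and indication of any on-study radiotherapy. Table 4 lists concomitant medications, but nothing in the documents shows that these radiotherapy details are captured.
3. State in Section 6.2 that an irradiated lesion cannot support CR.
4. In Section 10, pre-specify sensitivity analyses beside the primary results. Report the ORR and the interim responder count with any patient irradiated before a first documented CR or PR counted as a non-responder. Report PFS and duration of response with on-study radiotherapy treated as an event.
5. Reconcile Sections 4.3, 4.3.3 and 6.2 on radiotherapy related to progression versus radiotherapy for symptoms. Which clinical rule should govern is for the sponsor and investigators.

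A patient-level rule is preferable to freezing the irradiated lesion at its last scan before radiotherapy. Before the cycle 3 assessment that scan may be the baseline one, so the frozen status would read as no increase and the patient could still count as a PR at the interim. The patient-level rule is conservative, because some irradiated patients would have responded anyway. For patients irradiated before a first response, the primary and sensitivity ORRs therefore bracket the answer.

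The cost is a few sentences, a small addition to data collection, and possibly a slightly lower CR rate and sensitivity ORR. No extra scans or patients are needed.

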4.4 Duration of Therapy & Early Withdrawal

Treatment may continue for up to one (1) year or until any of the following occur, resulting in early withdrawal from study treatment (or in some cases withdrawal from the study as a whole):

- disease progression
- inter-current illness that prevents further administration of treatment
- unacceptable toxicity
- patient decides to withdraw from study treatment (or study as a whole)
- general or specific changes in the patient's condition render the patient unacceptable for further treatment in the judgment of the treating investigator

Note: Patients who have not achieved PR or CR after 4 cycles should continue to be treated on the current protocol only if they have SD (i.e., not PD), AND if they do not have other options available that would present a more favorable risk/benefit ratio.

Patients will be removed (withdrawn) from study therapy for any of the criteria listed above. The PI and the Quality Assurance Monitor (QAM) at NU is to be notified of such events; the reason(s) for removal and the date the patient was removed are to be documented in the appropriate electronic case report form (eCRF). The patient should be followed as described below in Section 4.5.

Patients who withdraw consent from the study as a whole will be noted to have withdrawn from both treatment and any further follow-up.

4.5 Duration of Follow Up

Once patients are off treatment for any reason, they will have a final off-treatment visit approximately 30 days post-last dose of study therapy. Thereafter, they will be followed with at least one clinic visit every 3 months for up to 1 year from start of treatment, then every 6 months up to 3 years from start of treatment (or until death, whichever occurs first). Patients removed from treatment for unacceptable adverse events will be followed until resolution or stabilization of the adverse event.

4.6 Patient Replacement

Any patient who is registered to the study and then withdrawn without receiving any study treatment may be replaced. Any patient who completes fewer than 2 total cycles of therapy and is withdrawn for any reason except POD or toxicity will still be considered evaluable for toxicity endpoints but will not be evaluable for efficacy endpoints; for the purpose of efficacy endpoints, another patient may be added to the accrual goal with the approval of the Data and Safety Monitoring Committee (DSMC) at NU.

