We propose proceeding with a phase II trial evaluating the safety and efficacy of the combination of romidepsin and lenalidomide in patients with previously untreated PTCL. The treatment population will include patients \geq 60 years of age who often have comorbidities that prevent the use of cytotoxic chemotherapy. In addition, the trial will enroll patients age \geq 18 years to < 60 years with a cumulative illness rating scale (CIRS) score \geq 6 or deemed ineligible for cytotoxic chemotherapy by the treating investigator. A CIRS score \geq 6 is a previously established cutoff to define increased treatment risk. The proposed dosing and schedule for romidepsin and lenalidomide are both FDA approved. The protocol will allow an increased dose of romidepsin from 10 mg/m² to 14 mg/m² pending tolerance assessment. The initial romidepsin dose of 10 mg/m² is chosen to avoid potential cytopenias with combination therapy. Up to 35 patients may be treated on the protocol in order to achieve a total of 20 evaluable. The trial will include a two-side design with an early assessment of futility following treatment of the first 12 patients with an early stopping point if 6 or fewer patients have a complete or partial response. Response will be determined by interval imaging; the 3 month response assessment time point will be used for the purposes of the interim efficacy analysis. Patients may be treated for up to 1 year or until progression of disease, intolerable toxicity, or withdrawal by patient.

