2.0 Study Objectives and Endpoints

2.1 Primary Objective & Endpoint

The primary objective of this phase II trial will be to evaluate the efficacy of the combination of romidepsin plus lenalidomide in patients with previously untreated PTCL.

The endpoint for this objective will be objective response rate (ORR), defined per Cheson criteria. Response will be assessed by imaging after cycles 3 and 6, and then every 6 months thereafter. Response at 3 months (after cycle 3) will be used for purposes of the interim efficacy analysis.

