6.0 Assessment of Endpoints

6.1 Toxicity Endpoints

The frequency and severity of adverse events will be assessed once per cycle according the NCI-CTCAE version 4.03. All patients who receive at least one dose of either study drug will be evaluable for toxicity endpoints.

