10.0 Statistical Considerations

10.1 Primary Endpoint & Sample Size Calculations

The primary objective of this phase II trial will be to evaluate the efficacy of the combination of romidepsin plus lenalidomide in patients with previously untreated PTCL. The endpoint for this objective will be objective response rate (ORR), defined per Cheson criteria. Response will be assessed by imaging after cycles 3 and 6, and then every 6 months thereafter. Single agent romidepsin or lenalidomide have response rates of approximately 25% in patients with relapsed/refractory PTCL [3, 44, 45]. However, a recently presented study (unpublished) of the combination of romidepsin and lenalidomide demonstrated an objective response rate in relapsed/refractory PTCL of 50%[46]. The front-line setting has not been tested.

Due to recruitment issues, we will limit the study to n=20 evaluable patients. This will allow us to estimate the underlying true response rate with a half width of an approximate 95% confidence interval equal to 1.96x0.5/sqrt(20) = 1.96x0.11 = 0.22.

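### Treated patients who stop before 2 cycles for reasons other than POD or toxicity drop out of the primary ORR, and no ORR in all treated patients is planned beside it

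*Combined protocol and SAP*

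**What the plan says.** Under Section 4.6, among patients who complete fewer than 2 cycles, anyone "withdrawn for any reason except POD or toxicity will still be considered evaluable for toxicity endpoints but will not be evaluable for efficacy endpoints". Another patient may then be added with DSMC approval. Early stops for POD or toxicity are not removed by this rule.

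The primary endpoint is ORR by Cheson criteria. On its analysis set, Section 10.1 says: "we will limit the study to n=20 evaluable patients". The Study Summary agrees, and Section 3.0 allows up to 35 to be accrued to reach that number.

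A set of all dosed patients exists, but only for safety. Section 6.1 says: "All patients who receive at least one dose of either study drug will be evaluable for toxicity endpoints". Sections 10.1 to 10.3 contain no ORR in that set, no sensitivity analysis of the denominator, and no rule for patients without a response assessment.

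Once POD and toxicity are set aside, the stopping reasons in Section 4.4 are "inter-current illness that prevents further administration of treatment", the patient's decision, and a change in condition that the investigator judges to rule out further treatment. For any removal, "the reason(s) for removal and the date the patient was removed are to be documented" in the eCRF.

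On timing, Section 2.1 says: "Response will be assessed by imaging after cycles 3 and 6, and then every 6 months thereafter". Section 4.5 adds: "Once patients are off treatment for any reason, they will have a final off-treatment visit approximately 30 days post-last dose of study therapy". Table 4 lists imaging at that visit; Section 4.5 itself does not mention it.

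**The concern.** The headline result is a single-arm response rate whose denominator depends on what happens after treatment starts. Illness or decline in the first two cycles can go with a poor response. Section 1.4 describes the patients aged 60 and over as people "who often have comorbidities that prevent the use of cytotoxic chemotherapy", so some early stops of this kind are plausible.

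The recorded reason for stopping also decides who is counted. A patient with confirmed POD in cycle 2 stays in the denominator. A similar patient who declines and stops without a confirming scan could be recorded under change in condition or patient decision, and would leave it.

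If the excluded patients respond less often than the rest, the evaluable-set ORR is too high. The plan requires no companion figure that would show by how much.

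**Working it through.** **The plan's own figure.** Half-width = 1.96 × 0.5 / √20 = 0.219, which rounds to the stated 0.22. It reproduces.

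**Timing.** The cutoff is 2 cycles (2 × 28 = 56 days). The first scheduled response scan follows cycle 3 (3 × 28 = 84 days). An excluded patient therefore has no scheduled on-treatment response scan. The off-treatment imaging in Table 4 could still document a CR or PR, except in a patient who withdraws from follow-up as well.

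**Inputs for the denominator.**
- Evaluable patients: 20 (Section 10.1).
- Responders r among them: 10, matching the 50% that Section 10.1 cites for the combination in relapsed/refractory disease, and 12 as a second illustration.
- Treated patients excluded under 4.6, k: not given. The cap of 35 for 20 evaluable bounds it at 35 − 20 = 15, but that bound also covers registrants who were never treated. The values 0, 2 and 5 below are assumptions.
- Documented responses among the excluded, j: not given; taken as 0 first, then varied.

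**Formula.** ORR in all treated = (r + j) / (20 + k), with Clopper-Pearson 95% intervals.

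| k (j = 0) | r = 12 | 95% CI | r = 10 | 95% CI |
|---|---|---|---|---|
| 0 | 12/20 = 60.0% | 36.1–80.9 | 10/20 = 50.0% | 27.2–72.8 |
| 2 | 12/22 = 54.5% | 32.2–75.6 | 10/22 = 45.5% | 24.4–67.8 |
| 5 | 12/25 = 48.0% | 27.8–68.7 | 10/25 = 40.0% | 21.1–61.3 |

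The drops are 5.5 and 4.5 points at k = 2, and 12 and 10 points at k = 5.

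**Responses among the excluded (k = 2).**
- r = 12: j = 1 gives 13/22 = 59.1%; j = 2 gives 14/22 = 63.6%.
- r = 10: j = 1 gives 11/22 = 50.0%; j = 2 gives 12/22 = 54.5%.

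The two sets agree when j = k × r / 20, that is 2 × 12 / 20 = 1.2 or 2 × 10 / 20 = 1.0 responses. The direction of the shift is therefore not fixed.

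**Precision.** By the plan's formula the half-width is 0.209 at n = 22 and 0.196 at n = 25, so the larger set loses no precision.

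**The case against.** An evaluable-set ORR is a common choice in a small single-arm phase II trial. Here the rule is explicit, prespecified and narrow, and adding a replacement patient needs DSMC approval. Section 4.0 asks that suspected progression be investigated by imaging or marrow biopsy, so much lymphoma-driven decline should be recorded as POD and stay in. At k = 2 the shift is about 5 points and the intervals overlap almost entirely. Section 10.1 is estimation only, so no final test result turns on it. All of this stands. It limits the size of the problem and supports keeping the evaluable-set ORR as primary. It does not supply the missing companion figure: a reader could work out the effect from treated N, evaluable N and all documented responses, but the plan does not require these to be reported together.

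Three stronger readings are tempting, and the documents support none of them.

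- **The cap implies 15 excluded treated patients.** With 10 responders that would give 10/35 = 28.6%. But 15 is only an upper bound, it includes patients never treated, and nothing suggests it will be reached.
- **The ORR is shown to be biased upward.** The documents give neither k nor the response rate among the excluded. There is no bias if nobody is excluded, or if the excluded respond as often as the rest.
- **The futility rule is undermined.** Section 7.4 counts the first 12 patients without saying treated or evaluable, and Section 1.4 places the look after 12 have been treated. However, Section 2.1 calls this look an efficacy analysis, and Section 4.6 takes the excluded patients out of efficacy endpoints. Together these largely settle it as evaluable patients. What remains is a point of wording.

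**Conclusion.** The point holds as a modest gap in the analysis plan. Following the text as written can inflate the headline ORR, and nothing planned would show it. Under the assumed range of 0 to 5 excluded patients with no responses among them, the difference runs from 0 to 12 points at 12 responders and from 0 to 10 points at 10 responders. The planned half-width is 22 points. The result rests on two unknowns, the number excluded and their responses, and the figures compare analysis sets rather than measure bias. The sample-size statement is correct as it stands.

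**What to change.** Keep the evaluable-set ORR as primary. In Section 10.1, add a prespecified sensitivity analysis: ORR with an exact 95% CI in all patients who received at least one dose of either study drug (the Section 6.1 population). Credit any documented CR or PR, including one on the off-treatment imaging in Table 4, and count patients without an assessment as non-responders. Report the number excluded under Section 4.6 with the reason for each.

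The cost is a short amendment. No new visits or data are needed, because removal reasons already go in the eCRF and the imaging is already scheduled. The companion ORR may be slightly lower, and it is conservative for unassessed patients; the text should say so. Making the all-treated ORR the primary figure is not proposed: at Amendment 11 of an open-label trial, a late change of the primary denominator would carry a credibility cost that a sensitivity analysis avoids.
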